5.6.5 Physical Examination

A physical examination, including vital signs measurements (blood pressure and pulse), will be performed at each study visit. Any clinically significant abnormalities discovered during physical

examinations after the Screening / Baseline (if occurring on the same day) visit should be documented and evaluated as potential adverse events.

5.6.6 Investigator Global Assessment (scalp only)

Investigator Global Assessment for scalp will be determined for all subjects throughout the study. Subjects are required to have a score of 2-mild or greater to enter the study. The Investigator Global Assessment is a 5 point scale that records disease severity based on average degree of erythema, induration and scaling. Investigator Global Assessment uses a scale of 0 = Clear, 1 = Almost Clear, 2 = Mild, 3 = Moderate, and 4 = Severe. [See Appendix A](#)

5.6.7 Psoriasis Scalp Severity Index (PSSI) and Scalp Surface Area (SSA)

The scalp is assessed for erythema, induration and desquamation. The average degree of severity of each 3 symptoms is assigned a score of 0-4. The surface area of scalp psoriasis is then estimated as a percentage. The PSSI score is the sum of the erythema, induration and desquamation scores multiplied by the area of involvement. Scores range from 0-72. [See Appendix B](#)

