Study Objectives	Primary Objective: To exploretheefficacyofTopicort®TopicalSprayatweeks4 and16 withrespectto Investigator GlobalAssessme nt(scalponly), Psoriasis ScalpSeverityIndex(PSSI) , andScalpSurfaceArea(SSA) Secondary Objectives: PGAxBSA,patient reportedoutcomes ,adverseevents
Study Design	A single center,observationalstudyof2 0subjectstoassess4weeksof therapy with Topicort® BIDand12weeks BIDontwoconsecutivedaysaweek patients with scalppsoriasis
Study Centers	PsoriasisTreatmentCenterofCentralNewJersey
Study Population	Adultmaleandfemalesubjectswithmoderatetoseverechronicplaque psoriasis
Main Inclusion Criteria	Subjectsmustmeetthefollowingcriteriatobenrolledinthisstudy: 1. Maleorfemaleadult \geq 18yearsofage; 2. Chronicscalppsoriasis \geq 30% 3. Investigator GlobalAssessment(scalponly) ofmildorgreater
Main Exclusion Criteria	Subjectswhomeetanyofthefollowingcriteriawillbeexcludedfrom participationinthisstudy: 1. Subjectswithnonplaquetypepsoriasis(e.g.guttate and erythrodermic). 2. Subjectswith<30%scalppsoriasis. 3. Useofprohibitedmedications duringstudyperiod.
Study Drug Dosage and Administration	Allpati entswillreceiveTopicort ® BIDfor4weeks. Afterweek4pat ientwillreceiveTopicort willreceiveTopicort® BIDontwo consecutivedaysaweek for12weeks . Patientswilltreatotherbodyareas affectedbyplaquepsoriasiswithTopicort®duringthestudyperiod(excludes face,groin,axilla)
Study Endpoints	Improvementafter 4and 16weeksof: InvestigatorGlobalAssessment(scalponly) PsoriasisScalpSeverityIndex Scalpsurfacearea Physician Global Assessment x Body Surface Area Pain,itching,scaling(scalponly) Scalpdex
Study Duration	16 weeks

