     1 2 3 4 5	     1 2 3 4 5	     1 2 3 4 5	     1 2 3 4 5 6

Scalp Surface Area

Record 0-100%

 %

Total PSSI score _____

PSSI SCORE = SUM OF SCORES FOR ERYTHEMA, THICKENING AND SCALING MULTIPLIED BY SCALP SURFACE AREA

(scores range from 0-72)

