Appendix F
Schedule of Assessments

Procedure	Screening	Enrollment	Week 4	Week 8	Week 16
Informed Consent	X				
Demographics/Medical History	X				
Inclusion/Exclusion	X	X			
Adverse Events	X	X	X	X	X
Concomitant Medications	X	X	X	X	X
Investigator Assessments	X	X	X	X	X
Urine Pregnancy Test	X	X			
Scalpdex		X	X		X
Pain Itching Scaling		X	X		X
IP dispense/accountability		X	X	X	X

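### PSSI signs are scored 0-4 in Section 5.6.7 but 0, 1, 3, 4, 5 on the Appendix B form, so the form reaches 90 while printing a range of 0-72

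*Combined protocol and SAP*

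**What the plan says.** The synopsis names three measures in the primary objective, assessed at weeks 4 and 16: scalp IGA, PSSI and scalp surface area.

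Section 5.6.7 defines the PSSI. On the signs it says "The average degree of severity of each 3 symptoms is assigned a score of 0-4". It has the area estimated as a percentage, and then says "The PSSI score is the sum of the erythema, induration and desquamation scores multiplied by the area of involvement. Scores range from 0-72". It attaches no verbal labels to the codes 0 to 4 and sends the rater to Appendix B.

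The Appendix B legend has the same five entries in all three sign columns: 0 None, 1 Slight, 3 Moderate, 4 Severe, 5 Very Severe. There is no 2. A fourth column gives an area score from 1 (<10%) to 6 (90-100%). Below the legend are tick boxes, a separate field for the raw percentage, and the formula "PSSI SCORE = SUM OF SCORES FOR ERYTHEMA, THICKENING AND SCALING MULTIPLIED BY SCALP SURFACE AREA", followed by "scores range from 0-72".

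Section 8.2 adds no scoring rule, and Section 8.2.1 only allows for a possible separate statistical plan.

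**The concern.** The text and the form it points to use different codes for the same three signs, yet both print the same total range. Only one of the two scales can give that range.

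The PSSI change to weeks 4 and 16 is a primary-objective result. The plan asks only for improvement and names no metric, but absolute change and percent change both depend on which printed scale the rater used. Two raters, or one rater at two visits, could follow different parts of the protocol and record different totals for the same scalp. A reader of the results could not tell which scale lay behind them. Entry requires at least 30% scalp involvement, which is area score 3 or more, so at screening every one-point coding difference in a sign is multiplied by at least 3.

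**Working it through.** **Inputs**

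- Section 5.6.7: three signs, each 0-4; stated total 0-72.
- Appendix B legend: sign codes 0, 1, 3, 4, 5; area score 1-6; stated total 0-72.
- Appendix B tick boxes, as they appear in the extracted text: 1-5 per sign. The area cell of that row shows five boxes for six numbers, so the row may not have extracted cleanly. Results that rest on it are provisional until the original form is checked.
- Formula in both places: (sign 1 + sign 2 + sign 3) × area.

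**Step 1: reproduce the stated range, then try the other readings**

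| Sign codes | Multiplier | Minimum | Maximum |
|---|---|---|---|
| 0-4 (Section 5.6.7) | area score 1-6 | 0 | (4+4+4) × 6 = **72** |
| 0, 1, 3, 4, 5 (legend) | area score 1-6 | 0 | (5+5+5) × 6 = **90** |
| 1-5 (boxes, used literally) | area score 1-6 | (1+1+1) × 1 = 3 | (5+5+5) × 6 = 90 |
| 0-4 | percentage 0-100 | 0 | 12 × 100 = 1,200 |
| 0, 1, 3, 4, 5 | percentage 0-100 | 0 | 15 × 100 = 1,500 |

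Only 0-4 signs with the 1-6 area score give 0-72. Section 5.6.7 nevertheless describes area only as a percentage, and the form's formula does not say which of its two area entries to use.

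**Step 2: how far the two code sets disagree, with no assumption about labels**

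- Five codes on three signs give 5³ = 125 combinations. On the legend, 125 − 4³ = 61 (48.8%) contain a 5, which Section 5.6.7 does not allow.
- On 0-4, 125 − 4³ = 61 contain a 2, which the legend does not offer.
- Of 125 × 6 = 750 sign-by-area combinations on the legend, 11 exceed 72: 10 at area score 6 with a sign sum of 13 or more, and 1 at area score 5 with a sign sum of 15. The values reached are 75, 78, 84 and 90.

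These are counts of possible combinations, not expected shares of patients.

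**Step 3: effect on a change score**

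Because Section 5.6.7 gives no labels, matching its codes to the legend's categories is an assumption. For all three signs going from Moderate to Slight at area score 3:

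| Mapping | Before | After | Change |
|---|---|---|---|
| (i) Labels in order on 0-4 (Moderate = 2, Slight = 1) | 3×2×3 = 18 | 3×1×3 = 9 | −9 (50%) |
| (ii) Legend codes (Moderate = 3, Slight = 1) | 3×3×3 = 27 | 3×1×3 = 9 | −18 (67%) |
| (iii) Labels in order on boxes 1-5 (Moderate = 3, Slight = 2) | 3×3×3 = 27 | 3×2×3 = 18 | −9 (33%) |

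Row (ii) would also hold on a 0-4 scale labelled like the IGA in Section 5.6.6 ("2 = Mild, 3 = Moderate, and 4 = Severe"). In that case Section 5.6.7 and the legend agree for this patient.

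**Step 4: size if mapping (i) is what Section 5.6.7 intends**

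The legend adds 0 for a sign that is None or Slight and 1 for a sign that is Moderate or worse, before multiplying by area. This is neither a constant shift nor a constant multiple, so taking percent change does not remove it. Combinations with at least one sign Moderate or worse number 125 − 2³ = 117 of 125 (93.6%). With all three signs Moderate or worse, the excess runs from 3 × 3 = 9 points at area score 3 to 3 × 6 = 18 at area score 6.

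**The case against.** The strongest reply is that the practical effect may be small. Totals above 72 need near-maximal signs over at least 70% of the scalp, while entry needs only mild disease and 30%. The study is exploratory, open-label and single-centre with 20 subjects, and it specifies no test. Both codings are ordered and the legend still gives 0 for a clear scalp, so consistent use of the legend would keep the direction of change for a single sign at fixed area. The legend has five ordered labels and Section 5.6.7 has five codes, so taking them in order is the natural match and the uncertainty can be overstated. The 1-6 score is plainly the intended multiplier, since a percentage would give totals far above 72.

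Much of this is fair. The maximum of 90 is a corner case. The multiplier needs a clearer wording and adds nothing to the arithmetic conflict. The box row should carry no weight until the original form is seen. If Moderate = 3 was intended, the differences shrink to the missing 2 and the extra 5. Inconsistent use between raters is possible but not shown.

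The central point still stands. A rater who follows the form as printed breaks the scale in Section 5.6.7 and the range on the form itself, and no other section resolves this. Under the in-order match, which the objection itself calls the natural one, the two codings give different scores for 117 of 125 sign combinations. A garbled extraction is an unlikely cause, because the skipped 2 and the top code 5 appear identically in three columns.

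**Conclusion.** The PSSI scoring is wrong as written and must be fixed before the PSSI is analysed. The maximum is 72 under Section 5.6.7 and 90 under the Appendix B legend, and the form prints 0-72. That needs no assumption beyond the 1-6 area score as multiplier, which is the only one that reproduces the stated range.

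The effect on an individual change score depends on the unlabelled match between codes and categories. In the worked case the fall is 50% or 67% on the two main readings, with no difference between text and legend if Moderate = 3 was meant. The 33% figure and the 3-90 range hold only if the tick boxes really run 1-5. The percentages also assume that improvement is analysed as percent change, which the plan does not say. Scalp IGA and the raw scalp surface percentage are unaffected.

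**What to change.** - Use one labelled scale of 0, 1, 2, 3, 4 for each sign in Section 5.6.7, the Appendix B legend and the tick boxes, with no 5. Check the box row on the original form and make sure it offers a 0.
- State in both places that the multiplier is the 1-6 Scalp Surface Area Score, and keep the raw percentage for the surface-area endpoint only. An area score of 0 is not needed, because zero signs already give a total of 0.
- Confirm the maximum as (4+4+4) × 6 = 72.
- For forms already completed, establish from source or from the rater which category each tick meant before recoding anything. Query every ticked 2 and any 1 that could mean None. If the rater is confirmed to have used the legend codes, they are distinct and ordered, so a documented one-to-one recode to the corrected in-order scale loses nothing. An unchecked automatic recode should not be applied.

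Before use, the cost is a one-page form correction and two sentences in Section 5.6.7, with no extra visits or patients. If forms exist, 20 subjects × 4 or 5 visits gives 80 to 100 forms, or 240 to 300 sign scores, depending on whether screening and enrollment fall on the same day. This assumes the PSSI is part of "Investigator Assessments" at every visit in Appendix F. Limited to baseline and weeks 4 and 16, which the stated endpoints use, it is 20 × 3 = 60 forms, or 180 sign scores.

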5.6.8 Physician's Global Assessment (PGA)

PGA will be determined for all subjects throughout the study. PGA is a 5 point scale that records the overall disease severity at each clinical evaluation based on the average degree of erythema, induration, and scaling of areas affected by psoriasis. PGA uses a scale of 0 = Clear, 1 = Almost Clear, 2 = Mild, 3 = Moderate, and 4 = Severe. [See Appendix C](#)

5.6.9 Body Surface Area (BSA)

BSA will be determined for all subjects throughout the study. The subjects palm will be selected for the measuring unit of body surface area. The physician will equate the number of palms affected by psoriasis to derive the BSA total.

5.6.10 Patient Reported Outcomes

Subjects will complete the Subject Assessment of Pain, Itching and Scaling and Scalpdex at weeks 0, 4 and 16. Scalpdex is a self-administered quality of life instrument developed for scalp dermatitis. The 23 item survey evaluates the subject across 3 major domains –symptom, functional and emotion.⁶ Pain, Itching and Scaling is a scale of 1-10 which assess pain, itch and scale in the past 24 hours. [See Appendix D and E](#)

5.6.11 Early Discontinuation Procedures

Subjects will be prematurely discontinued from the study under the following conditions:

1. Subject requests to withdraw from the study.
2. Subject is noncompliant with protocol schedule, restrictions, and/or requirements.
3. Subject experiences an adverse event that makes it difficult or intolerable for the subject to continue treatment, or increases risk to the subject, or interferes with the investigator's ability to clinically evaluate the progress of the subject's treatment.
4. Subject begins an unapproved concomitant therapy for psoriasis or another medical condition that may increase risk to the subject if continuing study treatment.
5. Subject cannot be reached / lost to follow-up.
6. The study investigator suspends or terminates the study.
7. Other unanticipated reason.

Any subject who prematurely discontinues the study should complete the week 16 (End of Study) assessments. Any subject who withdraws consent to participate in the study will be removed from further treatment and/or study observation immediately upon the date of request.

6 Adverse Events

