Appendix G

Dosing Diaries

	Date (MMM/DD)	Dose (Circle One)	Time (HH:MM)	Remark
Ex	Jan/01	AM / PM	0800	
	Jan/01	AM / PM	1030	
1		AM / PM		
2		AM / PM		
3		AM / PM		
4		AM / PM		
5		AM / PM		
6		AM / PM		
7		AM / PM		
8		AM / PM		
9		AM / PM		
10		AM / PM		
11		AM / PM		
12		AM / PM		
13		AM / PM		
14		AM / PM		
		AM / PM		

	Date (MMM/DD)	Dose (Circle One)	Time (HH:MM)	Remark
15		AM / PM		
		AM / PM		
16		AM / PM		
		AM / PM		
17		AM / PM		
		AM / PM		
18		AM / PM		
		AM / PM		
19		AM / PM		
		AM / PM		
20		AM / PM		
		AM / PM		
21		AM / PM		
		AM / PM		
22		AM / PM		
		AM / PM		
23		AM / PM		
		AM / PM		
24		AM / PM		
		AM / PM		
25		AM / PM		
		AM / PM		
26		AM / PM		
		AM / PM		
27		AM / PM		
		AM / PM		
28		AM / PM		
		AM / PM		

Extension (if needed)

	Date (MMM/DD)	Dose (Circle One)	Time (HH:MM)
29		AM / PM	
		AM / PM	
30		AM / PM	
		AM / PM	
31		AM / PM	
		AM / PM	
32		AM / PM	
		AM / PM	

Subject # _____ Initials: _____

Storage

- Keep study medication at room temperature.
- Keep out of reach of children

Dosing

- Administer twice daily (approximately 12 hours apart).
- Do not apply on face, underarms or groin
- Avoid heat, flames or smoking when applying.
- Do not bandage, cover, or wrap the treated area
- Spray only enough to cover affected area and rub in.
- Avoid bathing, showering or swimming right after applying the study medication.

Dosing Diary

- Record all doses on the diary as soon as possible.
- Return diary and medication to all of your appointments.
- Record any comments or information in "remarks" section for missed dose, adverse event, or change in medication.
- Please make recordings clear and legible.

	Date (MMM/DD)	Dose (Circle One)	Time (HH:MM)	Remark
Ex	JAN/01	AM / PM	08:30	
	JAN/01	AM / PM	08:00	
Ex	JAN/02	AM / PM	09:00	
	JAN/02	AM / PM	09:30	
Week 4 Day 1		AM / PM		
		AM / PM		
Week 4 Day 2		AM / PM		
		AM / PM		
Week 5 Day 1		AM / PM		
		AM / PM		
Week 5 Day 2		AM / PM		
		AM / PM		
Week 6 Day 1		AM / PM		
		AM / PM		
Week 6 Day 2		AM / PM		
		AM / PM		
Week 7 Day 1		AM / PM		
		AM / PM		
Week 7 Day 2		AM / PM		
		AM / PM		

EXT 1		AM / PM	
		AM / PM	
EXT 1		AM / PM	
		AM / PM	
EXT 2		AM / PM	
		AM / PM	
EXT 2		AM / PM	
		AM / PM	
EXT 3		AM / PM	
		AM / PM	
EXT 3		AM / PM	
		AM / PM	

Subject # _____ Initials: _____

APPLY TWO CONSECUTIVE DAYS A WEEK

Storage

- Keep study medication at room temperature.
- Keep out of reach of children

Dosing

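### Could exit readings from subjects who stop early be counted as week-16 results?

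*Combined protocol and SAP*

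**What the plan says.** Section 5.6.11 opens with "Subjects will be prematurely discontinued from the study under the following conditions" and lists seven conditions. It then states: "Any subject who prematurely discontinues the study should complete the week 16 (End of Study) assessments". No time is attached. The next sentence deals separately with a subject who withdraws consent, who "will be removed from further treatment and/or study observation immediately upon the date of request". Item 5 of the list is "Subject cannot be reached / lost to follow-up".

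Other places bear on the point:

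- Synopsis, Study Endpoints: "Improvementafter 4and 16weeksof" (word spacing lost in the PDF text), that is, improvement after 4 and 16 weeks.
- Section 5.6.10: "Subjects will complete the Subject Assessment of Pain, Itching and Scaling and Scalpdex at weeks 0, 4 and 16".
- Appendix F: columns for Screening, Enrollment, Week 4, Week 8 and Week 16, with no early-termination column and no visit windows.
- Section 8.2: about 20 subjects and a list of variables, with no analysis set, missing-data rule or rule for exit data.
- Section 8.2.1: a separate statistical plan is optional, and none is among the documents.

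**The concern.** Subjects are discontinued from the study and not only from treatment, so the natural reading is that the assessments are done on leaving. A subject who leaves early then gives an End of Study reading before week 16 and never gives one at week 16. For pain, itching, scaling and Scalpdex, the only scheduled slot after week 4 is week 16, which makes misfiling easy.

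This design makes timing matter. Dosing changes after week 4, and week 16 is the only primary time point at the end of the 12-week two-days-a-week phase. An exit reading shortly after week 4 follows very little of that phase. If such readings were pooled with true week-16 values, a reader could not tell whether the week-16 figure describes completers or a mixture.

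The sentence also says any subject, yet the next sentence removes consent withdrawers at once, and a subject lost to follow-up cannot attend.

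**Working it through.** **1. What the sentence can mean.** There are three readings: assess at exit, assess at calendar week 16, or carry out the procedures listed in the Week 16 column. The third is compatible with the first and has support in Appendix F. The Week 8 column omits Scalpdex and the pain, itching and scaling form, and the Week 16 column includes both. Naming that column is a short way to ask for the full set. It says which procedures to do. It does not say how to label the data, and no case report form is available to show otherwise.

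**2. Whom it covers.** Of the seven conditions, items 2, 3, 4, 6 and 7 clearly allow an exit assessment. Item 1 does if the request is not a withdrawal of consent. Item 5 cannot. The consent sentence is a specific exception to a general instruction, so there is no working conflict.

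**3. How different an early exit reading is.** The second phase (section 5.5.1.2) has 12 weeks × 2 days × 2 applications = 48 applications. In elapsed weeks from first dose, with the second phase starting on day 29:

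- exit at 5 weeks: 1 × 4 = 4 of 48 = 8.3%;
- exit at 8 weeks: 4 × 4 = 16 of 48 = 33.3%.

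The diaries label these 12 weeks Week 4 to Week 15, so 5 elapsed weeks is the end of diary Week 4.

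**4. Effect on a mean if exit readings were misfiled.** Let *m* be the mean improvement of true week-16 readings, *k* the number of exit readings, and *r* their mean improvement relative to *m*. With 20 subjects the pooled mean is *m*[(20 − *k*) + *kr*]/20 = *m*[1 + *k*(*r* − 1)/20]. The documents give neither *k* nor *r*. Assume *k* = 0 to 4 and *r* = 0.5 to 1.5:

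- *k* = 0: no change;
- *k* = 1: 1 × (±0.5)/20 = ±2.5% (relative);
- *k* = 4: 4 × (±0.5)/20 = ±10%.

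**5. Effect on a response rate.** For illustration, take 4 exits and 8 responders among 16 completers, with exact 95% intervals:

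| Handling of the 4 exits | Rate | 95% interval |
|---|---|---|
| Left out | 8/16 = 50% | 24.7% to 75.3% |
| All non-responders | 8/20 = 40% | 19.1% to 63.9% |
| All responders | 12/20 = 60% | 36.1% to 80.9% |

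The two extremes differ by 4/20 = 20 points. The completers-only interval alone spans 75.3 − 24.7 = 50.6 points.

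**6. Whether a written rule would do better.** The obvious strict rule is a visit window with zero improvement for anyone outside it.

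- *Zero improvement.* The mean becomes *m*(20 − *k*)/20, which is 5% lower at *k* = 1 and 20% lower at *k* = 4. Both shifts are twice the largest misfiling shift in step 4.
- *A window of days 105 to 133.* The early edge would rest on 11 × 4 = 44 of 48 applications, and the late edge on 112 + 3 × 7 = 133 days. The diaries in Appendix G do not fit either edge. The daily diary allows extension days 29 to 32. If the second phase starts on day 33, then 105 − 32 = 73 days (10 weeks and 3 days) have passed by day 105, which guarantees only 10 × 4 = 40 applications. Both two-days-a-week diaries have three extension weeks, so there is room to day 28 + 4 + 28 + 21 + 56 + 21 = 158. A completer seen after day 133 would be scored as zero improvement despite having a real final reading.

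**The case for a change.** The best case for a change is that neither timing gives a clean week-16 value and nothing in the documents closes the gap. At exit, the reading is early. At calendar week 16, section 5.5.1.4 has moved the subject to standard care, so the reading may reflect another therapy. Scalpdex asks about the past 4 weeks, so at a 5-week exit three of those four weeks lie in the daily phase. The optional statistical plan cannot be relied on, and labelling an exit visit and recording its study day would cost almost nothing.

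Most of this stands as description. The timing is unstated, Appendix F has no exit column, and section 8.2 is silent. What does not follow is that the plan gives a wrong result. The harm needs exit readings to be analysed as week 16, which no text says and which the endpoint wording points away from. That an exit reading soon after week 4 mainly reflects daily dosing is plausible, but no data in the documents support it. The choice among observed results, zero improvement and a particular window is one on which reasonable statisticians differ.

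**Conclusion.** No change to the plan is called for. This is missing detail that an analyst fills sensibly: take the reading by its actual study day, show week-16 results as observed with their n, and list early exits with their readings separately. That assumes visits are dated in the source records, as is usual. A separate label for the exit visit would be tidy housekeeping, but no conclusion depends on it.

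The stake is clarity of reporting. The effect on mean improvement is zero if nobody exits early. It is at most 2.5% (relative) for one exit and 10% for four, with unknown direction. These figures rest on assumed values of *k* and *r*, because the documents give no dropout rate and no outcome data. More or larger departures would increase them in proportion. With one arm, about 20 subjects, an exploratory aim and no stated hypothesis test, no error rate is involved.
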